5.2.5.4 Primary Analysis of Secondary Endpoint (Overall Survival)

The analysis of OS is based on the FAS. The number and percentage of participants experiencing an OS event and Kaplan-Meier plots of OS will be presented. The median OS and 2-sided 80% and 95% CIs will be estimated using the Kaplan-Meier method (if participant numbers allow).

Summaries of the number and percentage of participants who have died, those still in survival follow-up, those lost to follow-up and those who have withdrawn consent will be provided.

A summary of the duration of follow-up for OS will be included using median (range). This is presented separately for censored and non-censored participants.

The proportion of participants alive at every 3 months (3, 6, 9, 12, etc.) and associated 2-sided 80% and 95% CIs will be estimated using the Kaplan-Meier method.

5.2.5.5 Sensitivity Analysis of OS Endpoint

A sensitivity analysis will also be conducted to assess the impact of COVID-19 related deaths on OS. That is, participants who had an OS event due to death where the primary or secondary cause of death was COVID-19 infection or COVID-19 infection was reported as a fatal AE, will be censored on the date of their COVID-19 infection related death. This sensitivity analysis will only be performed if 5 or more participants have confirmed or suspected COVID-19 death events.

5.3 Pharmacodynamic Endpoints CCI

Analysis on pharmacodynamic CCI will be described in a separate analysis plan.

5.4 Pharmacokinetics – Module 1

This section covers details related to PK endpoints and analyses. PK is a secondary endpoint for Module 1.

5.4.1 Definition and Derivations

5.4.1.1 Plasma

The PK parameters of the concentration data for AZD4573 and its metabolites (if applicable) will be derived using non-compartmental methods in Phoenix® WinNonlin® Version 8.1 or higher (Certara) as data applicable.

The PK parameters will be calculated/estimated according to AstraZeneca standards.

PK analysis will, where data allow, be carried out using actual elapsed times determined from the PK sampling and dosing times recorded in the database. If actual elapsed times are missing, nominal times may be used. Nominal sampling times may be used for any agreed interim PK parameter calculations and PK parameters will be derived using standard non-compartmental methods.

For AZD4573 (intravenous [IV] infusion) the following PK parameters will be calculated using the PK concentration vs. time data from Cycle 1, Day 1 of Weeks 1 through 3 and Cycle 2, Day 1.

C _{max}	Maximum observed plasma (peak) drug concentration
t _{max}	Time to reach peak or maximum observed concentration following IP administration
λ _z	Terminal rate constant, estimated by log-linear least squares regression of the terminal part of the concentration-time curve
t _{1/2}	Half-life associated with terminal slope (λ _z) of a semi-logarithmic concentration-time curve
AUC(0-24)	Area under the plasma concentration-time curve from 0 to time 24 hours
AUC _{last}	Area under the plasma concentration-time curve from zero to last quantifiable concentration

AUC _{inf}	Area under plasma concentration-time curve from zero to infinity
CL	Total body clearance of drug from plasma after a single IV infusion dose
V _z	Volume of distribution after a single IV infusion (based on terminal phase)
V _{ss}	Volume of distribution at steady-state after a single IV infusion
t _{last}	Time of last observed (quantifiable) concentration
C _{max} /D	Dose-normalised C _{max}
AUC _{last} /D	Dose-normalised AUC _{last}
AUC _{inf} /D	Dose-normalised AUC _{inf}

Additional PK parameters may be determined where appropriate.

The following diagnostic parameters for plasma PK analysis will be provided:

λ_z lower	Lower (earlier) t used for λ_z determination
λ_z upper	Upper (later) t used for λ_z determination
$\lambda_z N$	Number of data points used for λ_z determination
R _{sq}	Statistical measure of fit for the regression used for λ_z determination
R _{sq} adj	Statistical measure of fit for the regression used for λ_z determination adjusted for the number of used data points (n obs)
λ_z span ratio	Time period over which λ_z was determined as a ratio of t _{1/2} / λ_z
AUC _{extr}	Extrapolated area under the curve from t _{last} to infinity (%)

The time period used for the estimation of apparent terminal elimination half-lives, where possible, should be over at least 2 half-lives. For t_{1/2} estimates where λ_z was calculated over a time period less than twice their resultant half-life, the reliability of t_{1/2} and any PK parameters derived from λ_z will be discussed in the CSR.

5.4.1.2 CCI

CCI
CCI

CCI

CCI
CCI
CCI
CCI
CCI
CCI
CCI
CCI

CCI
CCI

CCI
CCI
CCI
CCI

CCI
CCI
CCI

5.4.2 Primary Analysis of Pharmacokinetics

5.4.2.1 Plasma

Plasma concentrations will be listed by actual and relative (to dose administration) sampling time. The following summary statistics will be presented for concentrations and PK parameters at each time point:

- n below LLOQ (only for concentrations)
- gMean (calculated as $\exp[\mu]$, where μ is the mean of the data on a logarithmic scale)

- Geometric CV% (gCV, calculated as $100 \times \sqrt{\exp(s^2) - 1}$ where s is the standard deviation of the data on a natural log scale)
- Gmean + gSD (gSD calculated as $\exp[s]$ where s is the standard deviation of the data on the natural log scale. Gmean + gSD calculated as $\exp(\mu+s)$)
- Gmean – gSD (calculated as $\exp(\mu-s)$)
- Arithmetic mean
- Arithmetic Std Dev
- Minimum
- Median
- Maximum
- Number of observations

In listings, concentrations below the LLOQ will be presented as BLQ. In listings and tables where terms BLQ or LLOQ are included, the LLOQ (numerical value) will be included in a footnote.

For the calculation of statistics, concentrations that are BLQ will be handled as follows at each timepoint:

- If $\leq 50\%$ of the concentrations are BLQ, all BLQ values will be set to LLOQ, and all descriptive statistics will be calculated.
- If $> 50\%$, but not all, of the concentrations are BLQ, the gMean, gCV, arithmetic mean, and arithmetic Std Dev will be reported as “NC” (not calculable). The maximum value will be reported from the individual data, and the minimum and median will be set as “BLQ”.
- If all concentrations are BLQ, no descriptive statistics will be calculated. “NA” (not applicable) will be presented for gCV and arithmetic SD, and “BLQ” will be presented for gMean, arithmetic mean, median, minimum, and maximum.

For PK concentration and parameter data, if there are < 3 values available at a timepoint, only the maximum, minimum and n will be reported; the remaining descriptive statistics will be reported as “NC”. Concentrations that are BLQ are considered a value.

Missing samples will be reported as “NS” (no sample) and excluded from analysis.

Source data will be used in all derived PK concentrations without prior rounding.

The following figures, in black and white, will be produced:

- Participant Profiles, Plasma Concentration Time Data – Linear Scale

- Participant Profiles, Plasma Concentration Time Data – Semi-logarithmic Scale
- Gmean (\pm gSD), Plasma Concentration Time Data
- Gmean, Plasma Concentration Time Data – Semi-logarithmic scale

Individual and spaghetti figures will be plotted using concentration versus actual time, and mean figures will be plotted using concentration time versus nominal time by PK day as needed.

The following rules will be followed with regards to the number of decimal places and presentation of data in the tables and listings for PK parameters:

- Individual PK parameters will be presented to 4 significant digits, with the exception of t_{max} , which will be presented to 2 decimal places.
- Parameters derived directly from source data (eg, C_{max}) will be reported with the same precision as the source data (if this is not 4 significant digits).
- The mean, gMean, median and Std Dev values will be reported to 4 significant digits, all other descriptive statistics will be reported to 3 significant digits except for gCV% which will be presented to one decimal place.
- For t_{max} , the minimum and maximum will be presented to 2 decimal places and all other descriptive statistics will be presented to 3 decimal places.
- Estimates and confidence intervals in the form of percentages will be presented to 2 decimal places.

Criteria for Handling Concentrations Below the Limit of Quantification or Missing Concentrations in Pharmacokinetic Analysis

For the non-compartmental analysis and individual plots, if a BLQ value occurs before the first measurable concentration, it will be assigned the value of 0, otherwise it will be treated as missing. The following rules apply with special situations defined below:

- Where 2 or more consecutive concentrations are BLQ at the end of the profile the profile will be deemed to have terminated and any further quantifiable concentrations will be set to missing for the calculation of PK parameters, unless they are considered to be a true characteristic of the profile of the drug.
- If an entire concentration-time profile is BLQ, the profile will be excluded from the PK analysis.
- If a pre-dose measurement for the first dose of Cycle 1 is missing, the value will be set to zero.

Treatment of Outliers in Pharmacokinetic Analysis

If a value is considered to be anomalous due to being inconsistent with the expected PK profile, it may be appropriate to exclude this point from the PK analysis. However, exclusion of data must have a strong justification and will be documented in the CSR.

Quantifiable predose concentration values in the first dosing of Cycle 1 will be considered anomalous and set to missing for the PK analysis.

5.4.2.2

CCI

CCI

5.5 Immunogenicity

No immunogenicity analysis will be conducted for Module 1.

5.6 Safety Analyses

The domain safety covers exposure, adverse events, clinical laboratory, vital signs, electrocardiograms (ECGs), B symptoms, and tumour lysis syndrome (TLS).

Tables will be provided for the safety analysis set; listings will be provided for All participants or the safety set depending on the availability of data.

All safety analysis will be presented by cohort.

5.6.1 Exposure

Exposure amounts, durations and dose modifications and interruptions/delays will be summarised for the following periods:

- Overall treatment period
- Cycle 1
- Up to first tumour assessment
- Cycle 2 onwards

5.6.1.1 Definitions and Derivations

- Total duration of exposure is defined by the last date of actual AZD4573 dosing (ie, a dose > 0 mg was given) plus 6 days (due to the fact that AZD4573 is ordinarily dosed on a weekly schedule) minus the date of first AZD4573 dose (> 0 mg) plus 1.
 - For participants who die whilst on study treatment or if a DCO occurs, duration of exposure (months/weeks) is defined as date of death/DCO (whichever occurs first) minus the date of first treatment plus 1 day.

- Therefore: Duration of exposure (weeks) = $[\min(\text{last dose date where dose} > 0 \text{ mg} + 6, \text{ date of death, date of DCO}) - \text{first dose date} + 1]/7$.
- Actual duration of exposure (weeks) = $[\text{duration of exposure (days)} - \text{total duration of dose delays (days)}]/7$. Duration of exposure is calculated as above, and dose delays are defined as any length of time where the subject has not taken any of the planned dose in accordance with the protocol. The actual exposure calculation makes no adjustment for any dose reductions that may have occurred.
- Dose intensity of study intervention is addressed by considering relative dose intensity (RDI), where RDI is the percentage of the actual dose delivered relative to the intended dose through to treatment discontinuation. More specifically, RDI is defined as follows:
 - $\text{RDI (\%)} = 100 \times d/D$, where d is the actual cumulative dose delivered up to the actual last day of dosing and D is the intended cumulative dose up to the actual last day of dosing. D is the total dose that would be delivered, if there were no modification to dose or schedule. Note: When accounting for the calculation of intended cumulative dose 2 days should be added to the date of last dose to reflect the protocol allowed window for dosing.
 - CCI
CCI
CCI
CCI
CCI
CCI
CCI
CCI
CCI
CCI
CCI
CCI
- Duration of dose delays will be derived for doses indicated as being delayed on the eCRF. For each individual dose, the duration of dose delay is the number of days the dose was received outside of the original planned dosing schedule. Overall duration of dose delays will be calculated as the sum of all individual dose delays during the study. For example, assume the eCRF indicate that there was a treatment delay (question “Treatment delayed” indicated as “Y” by investigator) then the duration of the individual delay will be $[\text{date first dose received after delay} - \text{date last dose received before delay} - 9]$. For example, if dose is given on days 1 and 15 with the eCRF indicating a delay, the duration of the delay = $15 - 1 - 9 = 5$ days.

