2.1.2 Study Design

[figure not shown]
Module 1 will assess the efficacy of AZD4573 as a monotherapy in r/r PTCL and r/r cHL populations. Module 1 is non-randomised and will consist of 2 r/r PTCL cohorts (non-natural killer [NK] PTCL and natural killer T-cell lymphoma [NKTCL]) and one r/r cHL cohort.

During the first cycle per the protocol, participants will normally receive a single dose of AZD4573 once weekly, beginning with intra-participant ramp-up doses of 6 mg and 9 mg in Week 1 and Week 2, respectively. This is then followed by the target dose level of 12 mg for each of Weeks 3 to 5. It should be noted, however, that it may take more than 5 weeks to complete 3 AZD4573 dose weeks at target level, due to missed dose weeks and/or by repeating lower (ramp-up) doses of AZD4573. For the purposes of analysis defined in this SAP, Cycle 1 is defined as having received 5 doses of AZD4573 (regardless of dose level).

Each cycle beyond Cycle 1 will be 3 weeks in length and participants are planned to receive 12 mg infusions of AZD4573 once weekly until progression.

The dosing regimen for Module 1 is presented in [Figure 1](#).

Figure 1 Module 1 AZD4573 Monotherapy Dosing Regimen in PTCL and cHL including Intra-Participant Dose Ramp-Up

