5.6.1.2 Presentation

Total and actual duration of exposure to study intervention in weeks will be summarised by descriptive statistics. Dose intensity will be summarised by descriptive statistics. Exposure to IP (ie, total amount of IP received) will be listed and summarised for all subjects. Exposure swimmer plot(s) will be produced, with a line presented for each subject to display relevant exposure and disposition details.

Dosing deviations for IP will be summarized with reasons for deviations for the following categories: reductions and interruptions. The number of subjects with dosing delays and total dose delays will be summarised. Dose delays will also be summarised for number of delays with a duration < 7 days and number of delays with a duration ≥ 7 days.

The following additional summaries will also be produced:

- Number of participants that completed Cycle 1 (ie, received 5 doses of AZD4573), including number of participants that did not complete Cycle 1.
- Number of doses received per participant in Cycle 1.
- Total and actual duration of exposure, specific to Cycle 1.
- Number of participants that initiated Cycle 2.

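### The dose-delay formula deducts 9 days from every flagged gap, which contradicts the SAP's own definition of a delay and its weekly exposure convention

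*SAP*

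**What the plan says.** SAP 5.6.1.1 contains four statements that bear on the length of a delay.

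- Definition: for each dose, "the duration of dose delay is the number of days the dose was received outside of the original planned dosing schedule".
- Trigger: "Duration of dose delays will be derived for doses indicated as being delayed on the eCRF". No minimum gap and no lower limit on the result are given.
- Formula: the date of the first dose after the delay, minus the date of the last dose before it, minus 9. The example is "if dose is given on days 1 and 15 with the eCRF indicating a delay", scored as 5 days.
- Use: actual duration of exposure is total duration minus the sum of the delays. Delays are described there as "any length of time where the subject has not taken any of the planned dose", and the sentence goes on to tie this to accordance with the protocol.

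Total duration runs from the first dose to the last dose "plus 6 days (due to the fact that AZD4573 is ordinarily dosed on a weekly schedule"), so the last dose is credited with a full week. SAP 2.1.2 gives the schedule: after Cycle 1, "participants are planned to receive 12 mg infusions of AZD4573 once weekly until progression"; Cycle 1 is also weekly.

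SAP 5.6.1.2 sets the reporting classes: "Dose delays will also be summarised for number of delays with a duration < 7 days", alongside the number lasting 7 days or more.

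The SAP amendment history (20 Nov 2023) records that the deduction was changed from 7 to 9 to reflect the ±2-day window.

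**The concern.** A tolerance window normally answers a yes/no question: was this dose late? Here it is also taken off the length of every delay that is counted. The verbal definition and the formula then give different answers for the SAP's own example. Delay length also no longer fits with total exposure, which is built on 7 days per dose.

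At stake are the tables that show how well weekly dosing was kept up. Actual exposure would be longer for a participant who skipped a week than for one who received the same number of doses on time. The 7-day cut-point, which equals the dosing interval, would not separate a skipped weekly dose from a short slip. Nothing in the text stops a delay from being negative.

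**Working it through.** **Inputs.** Dosing interval 7 days (SAP 2.1.2). Deduction 9 days, flag-only trigger, last dose + 6 days, actual = total - delays (all SAP 5.6.1.1). Class boundary 7 days (SAP 5.6.1.2).

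**Step 1: the plan's own figure.** 15 - 1 - 9 = 5 days. It reproduces.

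**Step 2: the same example under the SAP's definition.** After a dose on Day 1 the next weekly dose is planned for Day 8. Given on Day 15, it is 15 - 8 = 7 days off schedule, not 5.

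**Step 3: effect on actual exposure.** For two doses a gap of g days apart, the second flagged as delayed:

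- total = (1 + g) + 6 - 1 + 1 = g + 7
- delay = g - 9
- actual = (g + 7) - (g - 9) = 16 days, whatever g is

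Two doses on schedule (Days 1 and 8, no flag) give total = actual = 14 days. The 2-day excess is 9 - 7 and recurs with each flagged delay.

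| Gap (days) | Total | Delay, minus 9 | Actual, minus 9 | Class, minus 9 | Delay, minus 7 | Actual, minus 7 | Class, minus 7 |
|---|---|---|---|---|---|---|---|
| 8 | 15 | -1 | 16 | < 7 | 1 | 14 | < 7 |
| 9 | 16 | 0 | 16 | < 7 | 2 | 14 | < 7 |
| 10 | 17 | 1 | 16 | < 7 | 3 | 14 | < 7 |
| 14 | 21 | 5 | 16 | < 7 | 7 | 14 | ≥ 7 |
| 15 | 22 | 6 | 16 | < 7 | 8 | 14 | ≥ 7 |
| 16 | 23 | 7 | 16 | ≥ 7 | 9 | 14 | ≥ 7 |
| 21 | 28 | 12 | 16 | ≥ 7 | 14 | 14 | ≥ 7 |

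In the 8-day row, actual exposure (16) exceeds total (15). The ≥ 7 class needs g - 9 ≥ 7, that is g ≥ 16.

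**Step 4: illustration over a longer course.** This pattern is assumed, not taken from the documents: 26 weeks with every fourth weekly dose skipped, giving 20 doses and 6 flagged 14-day gaps. Total is 182 days. With 9, delays are 6 × 5 = 30 and actual is 152. With 7, delays are 6 × 7 = 42 and actual is 140, which equals 20 × 7. The excess is 12 days, or 12/140, about 9%.

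**Step 5: does the formula measure days beyond the window?** Take doses planned for Days 8 and 15 but given on Days 6 and 17. Each is within ±2 days, so days beyond the window are 0. If the second is flagged, the formula gives 17 - 6 - 9 = 2. It counts from the previous actual dose, so it does not consistently measure days beyond the window either.

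**The case against.** The strongest reply is that 9 is a recorded choice, not a slip. The protocol allows ±2 days, the relative dose intensity derivation in the same section adds the same 2 days, and the actual-exposure text ties delays to the protocol. On that reading a delay means days beyond the permitted window, and 5 is the right answer for Days 1 and 15. This stands to the extent that the arithmetic is sound and the excess of 2 days is relative to the weekly convention. It does not rescue the formula. The section also defines delay against the planned schedule, the formula does not implement days beyond the window (step 5), and it has no floor.

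Three stronger readings are tempting but not supported:

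- *A single missed weekly dose always lands in the under-7 class.* It does for 14- and 15-day gaps. With doses on Days 1 and 17, one dose is missed and the next is within its window, yet the gap is 16 and the delay is 7.
- *The change to 9 brings back the problem that the amendment set out to cure.* The amendment history lists the actual-exposure update (actual longer than intended) and the 7-to-9 change in separate rows. Actual exceeds total only for flagged gaps of 8 days or less; in the SAP's example actual is 16 against a total of 21.
- *The tolerability conclusion is compromised.* The safety endpoints in SAP 2.1.1 are adverse events, laboratory data, vital signs and ECG. Missed dosing also shows in relative dose intensity, total product received, doses received in Cycle 1, swimmer plots and adverse events leading to dose delay.

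Negative delays need an investigator to flag a dose given 8 days or less after the last. The eCRF completion rules are not in the documents, so how often that would happen is unknown.

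**Conclusion.** The concern holds as an internal inconsistency. The formula in SAP 5.6.1.1 disagrees with that section's definition of a delay and with the week credited to the last dose in total exposure. Relative to the weekly convention, each flagged delay is 2 days too short and actual exposure 2 days too long. Flagged gaps of 8 days or less give negative delays, and an exact one-week skip is classed below 7 days.

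This rests on the planned interval being 7 days, on the eCRF flag being the only trigger, and on the absence of a stated floor. The effect is confined to descriptive delay and actual-exposure summaries. ORR, PFS and OS do not use these quantities. It is worth correcting, but it does not threaten the trial's main results.

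**What to change.** Use the ±2-day window only to decide whether a flagged dose counts as delayed. If it is within the window, set the length to 0. If it counts, set the length to the gap minus 7 days, or to the days from the planned dose date, with a minimum of zero. Correct the worked example to 15 - 1 - 7 = 7 days and keep the two reporting classes.

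Measuring from the planned date is the more exact option: for doses on Days 6 and 17, gap minus 7 gives 4, although the second dose was 2 days after its planned date. If that option is chosen, the SAP should say how planned dates are set after a skipped week.

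The cost is one SAP line and one program line. There is a downside. With the window applied to the gap, the length steps from 0 at 9 days to 3 at 10 days. In-window slips of 1 to 2 days also stay in actual exposure: gaps of 8 and 9 days give 15 and 16 days, and only longer gaps return to 14.

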5.6.1.2 Presentation

Total and actual duration of exposure to study intervention in weeks will be summarised by descriptive statistics. Dose intensity will be summarised by descriptive statistics. Exposure to IP (ie, total amount of IP received) will be listed and summarised for all subjects. Exposure swimmer plot(s) will be produced, with a line presented for each subject to display relevant exposure and disposition details.

Dosing deviations for IP will be summarized with reasons for deviations for the following categories: reductions and interruptions. The number of subjects with dosing delays and total dose delays will be summarised. Dose delays will also be summarised for number of delays with a duration < 7 days and number of delays with a duration ≥ 7 days.

The following additional summaries will also be produced:

- Number of participants that completed Cycle 1 (ie, received 5 doses of AZD4573), including number of participants that did not complete Cycle 1.
- Number of doses received per participant in Cycle 1.
- Total and actual duration of exposure, specific to Cycle 1.
- Number of participants that initiated Cycle 2.

